	Day -28 to -1	Day 1 Until Discontinuation of Treatment (\pm 3 days); See Notes	See Notes	Visit 30 Days After Last Treatment (\pm 5 days)	Phone Call 90 Days After Last Treatment (\pm 5 days)	Phone Call Every 12 weeks (\pm 2 weeks)	
Treatment Phase: Participants entering this rollover study on active treatment with bintralusp alfa in a parent study should begin Day 1 treatment under the rollover protocol according to the interval and dosing schedule in the parent protocol.
 
End of Treatment: Visit should be held within 30 days of last treatment for participants discontinuing due to AEs. For all others, visit should be held within 7 days of last treatment or prior to any new antineoplastic therapy, whichever is earlier.

Pregnancy test		Day 1 of every other cycle		X			The β -hCG pregnancy test should be determined from either a urine or serum sample according to local practice.
Skin assessment	X	Every 6 weeks	X	X			See Section 8.3.6.3.
Weight		Participants on mg/kg dosing: Day 1 of each cycle; Participants on flat dose: according to SOC					Cycle length determined based upon treatment cycle duration from parent protocol. For participants continuing to receive bintralusp alfa doses based on their weight (mg/kg dosing), body weight should be determined prior to bintralusp alfa administration.
Height	X						
ECG		According to SOC and institutional guidelines					
Hematology							See Section 8.2.4 and Appendix 6 for further details. Blood samples must be drawn prior to dosing and results of selected laboratory tests (see Appendix 6) must be reviewed within 3 days prior to dosing.
Biochemistry							
Urinalysis							
Free T4 and TSH		Every 6 weeks		X			

Assessments and Procedures	Eligibility Visit	Treatment Phase	End of Treatment	Safety Follow-up	Long-term Follow-up	Notes

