Category	Criterion
Sex and Contraception/Barrier Requirements	
3. The allowed sex/sexes for the study:
 
• Male• Female 
The investigator confirms that each participant agrees to use appropriate contraception and barriers, if applicable. The contraception, barrier, and pregnancy testing requirements are below. For female participants of childbearing potential or for male participants who have female partners of childbearing potential, the following applies:
 
Participants on active treatment must agree to continue to use highly effective contraception (i.e., methods with a failure rate of less than 1% per year; see Appendix 3) for both male and female participants if the risk of conception exists (Note: The effects of the study intervention on the developing human fetus are unknown (refer to Section 2.3.1); thus, women of childbearing potential and men must agree to use highly effective contraception as stipulated in national or local guidelines). Highly effective contraception must be used 28 days prior to the first study intervention administration, for the duration of study intervention, and at least for 2 months (for female participants) or 4 months (for male participants) after stopping study intervention. Should a woman become pregnant or suspect she is pregnant while she or her partner is participating in this study, the treating physician should be informed immediately.

Informed Consent	4. Capable of giving signed informed consent, as indicated in Appendix 2 , which includes compliance with the requirements and restrictions listed in the informed consent form (ICF) and this protocol.

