6.7 Reinitiation Criteria

For participants who discontinue bintrafusp alfa treatment during this rollover study, one reinitiating course of treatment at the same dose and schedule is allowed at the discretion of the Investigator and with agreement of the Study Medical Responsible:

- Participants who enter into this rollover study on active treatment will be eligible for one reinitiating course of treatment during this rollover study, regardless of whether or not they reinitiated treatment in a parent study.
- Participants who reinitiate treatment with bintrafusp alfa at study entry into this rollover study will be eligible for one more reinitiation (second reinitiation) if treatment is discontinued during this rollover study.

The following participants are eligible for reinitiation:

- Participants who are experiencing a CR, a PR, or SD at the time of treatment discontinuation in the rollover study, and then subsequently develop disease progression after stopping therapy, but prior to the end of the study.
- Participants who discontinue from treatment in the rollover study due to an AE that is subsequently well managed or resolved, as assessed by the Investigator, prior to the end of the study.

The participant should reinitiate treatment at the treatment phase visit where they left off according to the SoA (see Section 1.3). Participants who reinitiate treatment should stay on study and should be treated and monitored according the SoA for the rest of the study.

Prior to reinitiation, the Investigator will need to confirm that the benefit of reinitiating treatment outweighs any risk involved, such as that which led to initial treatment discontinuation. For participants with only SD at the time of discontinuation, the Investigator should confirm that no other reasonable treatment options are available. In addition, to be eligible for reinitiation, the participant must not have previously withdrawn consent for this study and should have been followed up with regular eCRF documented evaluation scans up to reinitiation of treatment.

A rebaseline scan must be performed prior to reinitiation of study intervention. Additionally, relevant safety laboratory assessments, including both full hematology and full chemistry results within 2 weeks, must be available and verified. The clinical Investigator will determine whether additional evaluation and work-up are required on a case-by-case basis.

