- g. Keratoacanthoma (KA) and cutaneous squamous cell carcinoma (cSCC).
- h. Grade 3 non tumor bleeding requiring intervention or hospitalization if alternative explanation can be identified (such as concomitant use of antithrombotic agents, traumatic event, etc.).

If persistent Grade 3 treatment-related AEs (excluding endocrinopathies controlled with hormone replacement therapy) either do not resolve or improve to Grade 1 within 12 weeks after last dose of study intervention, treatment must be permanently discontinued. If a Grade 2

treatment-related TEAE improves to Grade ≤ 1 or completely resolves by the day before the next infusion, study intervention may be continued.

Grade 2 treatment-related TEAE

If a Grade 2 treatment-related TEAE does not improve to Grade 1 or completely resolve by the day before the next infusion, but it is manageable and/or not clinically relevant, the Medical Monitor should be consulted to assess if it is clinically reasonable to administer the following infusion. In any case, if ≥ 2 doses are missed due to AE, the Medical Monitor should be consulted.

Immune-related AEs, IRRs, anemia, TGF β inhibition mediated skin reactions, and bleeding AEs

Permanent study intervention discontinuation may be recommended, so the relevant section must be reviewed:

- For suspected irAEs, general guidance and management are provided in [Section 8.3.6.2](#). Recommended guidance and management for specific irAEs as per published guidelines is provided in the current National Comprehensive Cancer Network (NCCN) guideline available at <http://www.nccn.org>.
- IRR and hypersensitivity reaction management guidance are presented in [Section 8.3.6.1](#).
- Anemia management guidance is presented in [Section 8.3.6.4](#).
- TGF β inhibition mediated skin reactions management guidance is provided in [Section 8.3.6.3](#).
- For guidance and management of bleeding AEs, see [Section 8.3.6.5](#).

If study intervention is permanently discontinued, the participant will remain in the study to be evaluated for the End of Treatment and Safety Follow-up. The Schedule of activity (see [Table 1](#)) indicates data to be collected at the time of discontinuation of study intervention and follow-up and for any further evaluations that need to be completed.

In case of discontinuation from the study intervention:

- The day of End of Treatment will correspond to the day of withdrawal (or within 7 days) for further details refer to [Table 1](#).

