8.2.4 Clinical Safety Laboratory Assessments

- Blood and urine samples will be collected for the clinical laboratory tests listed in [Appendix 6](#) at the time points listed in the SoA ([Table 1](#)). All samples will be clearly identified.

-
- Additional tests may be performed at any time during the study, as determined necessary by the Investigator or required by local regulations.
 - The tests will be performed by the local laboratory.

The Sponsor will receive a list of the local laboratory normal ranges before shipment of study intervention(s). Any changes to the ranges during the study will be forwarded to the Sponsor or designated organization.

The Investigator will review each laboratory report, document this review, and record any clinically relevant changes occurring during the study in the AE section of the CRF. The laboratory reports will be filed with the source documents.

8.3

Adverse Events and Serious Adverse Events

The definitions of an AE and a SAE are in [Appendix 4](#) Adverse Events: Definitions and Procedures for Recording, Evaluating, Follow-up and Reporting.

The Investigator and any qualified designees (e.g., Sub-Investigators) are responsible for detecting, documenting, and recording events that meet the definition of an AE or SAE. The Investigator remains responsible for following up AEs that are serious or that caused the participant to discontinue the study intervention as specified in [Section 8.3.3](#).

Requests for follow-up will usually be made via the Study Monitor, although in exceptional circumstances the global patient safety department may contact the Investigator directly to obtain further information or to discuss the event.

8.3.1

Time Period and Frequency for Collecting Adverse Event and Serious Adverse Event Information

- All AEs will be collected from the signing of the ICF until 90 days as specified in the SoA.
- All SAEs will be collected from the signing of the ICF until 90 days of last dose of the study treatment at the time points specified in the SoA ([Table 1](#)). Beyond this reporting period, any new unsolicited SAEs that the Investigator spontaneously reports to the Sponsor will be collected and processed.

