Appendix 6 Clinical Laboratory Tests

Protocol-Required Clinical Laboratory Assessments

Laboratory Assessments	Parameters		
Hematology	Platelet count ^d	Mean corpuscular volume (MCV)	White blood cell (WBC) Count with Differential ^d : 
 • Neutrophils • Lymphocytes • Monocytes • Eosinophils • Basophils
	Reticulocytes (%)	Mean corpuscular hemoglobin concentration (MCHC)	
	Hemoglobin ^d	Mean corpuscular hemoglobin (MCH)	
	Hematocrit	Activated partial thromboplastin time (aPTT) ^a	
	Red blood cell count ^d	Prothrombin time ^a	
	Absolute lymphocyte count ^d	International normalized ratio (INR) ^a	
	Absolute neutrophil count ^d		
Biochemistry	Blood Urea Nitrogen/Total urea	Potassium	Aspartate Aminotransferase ^d Bilirubin (total, indirect/direct) ^d
	Creatinine ^d	Sodium	Alanine Aminotransferase ^d Total Protein
	Glucose	Calcium	Alkaline phosphatase Tuberculin skin test, QuantiFERON-TB-Gold, or T-SPOT
	Lipase	Chloride	Albumin
	C-reactive protein	Amylase	
Routine Urinalysis	Physical appearance (color and transparency) 
 • Specific gravity by dipstick • pH, glucose, protein, blood/hemoglobin, ketones, bilirubin, urobilinogen, nitrite, leukocytes by dipstick Microscopic examination (if blood or protein is abnormal). Urine culture by suspicion of urinary tract infection		
Other Screening Tests	
 • Follicle-stimulating hormone (FSH) and estradiol (as needed if not a woman of childbearing potential [WOCBP] only) • Serum or highly sensitive urine human chorionic gonadotropin (hCG) pregnancy test (WOCBP only) • Hepatitis Screening^b: Hepatitis B surface antigen; Hepatitis B core antibody and Hepatitis C antibody • HIV; HIV virus RNA, quantitative; and CD4 lymphocyte count^c 		

^a Coagulation parameters collected at Baseline and as clinically indicated, thereafter (See Table 1).

^b As clinically indicated in participants with a history of hepatitis B virus (HBV) or hepatitis C virus (HCV) infection. If hepatitis B surface antigen positive and hepatitis B core antibody positive, then reflex to quantitative HBV DNA polymerase chain reaction (PCR); if hepatitis B core antibody positive alone, then reflex to quantitative hepatitis B DNA (PCR); if hepatitis C antibody positive, then reflex to quantitative hepatitis C RNA (PCR).

Laboratory Assessments	Parameters

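### No pregnancy test is expressly required before the first dose of a course restarted within the rollover study; on an off-test cycle the last scheduled test may be the 30-day post-treatment one

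*Protocol*

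**What the plan says.** **Testing schedule.** In Table 1 (Protocol 1.3) the pregnancy row reads "Day 1 of every other cycle" for the treatment phase and has one further mark, at the 30-day Safety Follow-up visit (±5 days). The Eligibility, End of Treatment, 90-day and long-term cells are empty. The table does not say which cycles are the tested ones, or how the alternation picks up after a break.

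**Restart rules.** Section 6.7 permits one reinitiating course within the rollover study and places it in the schedule as follows: "The participant should reinitiate treatment at the treatment phase visit where they left off according to the SoA". The preconditions are a rebaseline scan, agreement of the Study Medical Responsible, a statement that "the Investigator will need to confirm that the benefit of reinitiating treatment outweighs any risk involved", and a laboratory requirement: "relevant safety laboratory assessments, including both full hematology and full chemistry results within 2 weeks, must be available and verified". Any further work-up is left to the Investigator, case by case. Section 8.3.6.3 adds a new baseline skin assessment for these participants.

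**Laboratory rules.** Section 8.2.4 collects the Appendix 6 tests "at the time points listed in the SoA", and its next bullet allows extra tests whenever the Investigator sees a need. Appendix 6 lists hCG under other screening tests, apart from hematology and biochemistry.

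**Contraception.** Section 5.1, criterion 3, requires highly effective contraception from 28 days before first administration, throughout study intervention, and "at least for 2 months (for female participants) or 4 months (for male participants) after stopping study intervention". It announces pregnancy-testing requirements, but the text that follows gives contraception rules only.

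**The concern.** Table 2 lists embryofetal toxicity as an important potential risk, and pregnancy is the first exclusion criterion. Section 7.1 bars dosing a participant known to be pregnant, and Section 8.3.5 stops study intervention or withdraws a participant who becomes pregnant. These provisions work only if someone knows of the pregnancy. On continuous treatment the alternate-cycle test supplies that knowledge at short intervals. After a treatment gap, a restart that falls on an off-test cycle has no scheduled test to supply it, although the required contraception may by then have ended.

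For this same situation the authors did name a repeat scan and a repeat skin assessment. The absence of a matching line for hCG therefore looks like an oversight.

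What is at stake is the safety of an individual participant and a possible fetus. The adverse-event tabulations and the overall survival analysis are not affected.

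**Working it through.** The plan states no figure to reproduce. The check is a reading of the schedule plus date arithmetic.

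**Inputs**
- Tests on Day 1 of alternate cycles, and at day 30 (25 to 35) after the last dose: Table 1.
- Cycle length 14 or 21 days: Table 4 and Section 4.3.
- Restart at the visit where the participant stopped: Section 6.7.
- Contraception minimum for women 2 months after stopping: Section 5.1. I take this as 61 days (assumption).
- Nominal dates; the ±3-day treatment window is ignored.

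**Step 1: continuous treatment.** The scheduled test is 0 days old on a test cycle and one cycle old on an off-test cycle. The maximum age at any dose is therefore 14 or 21 days.

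**Step 2: does an off-test restart occur?** The place where treatment stopped could mean the next visit in sequence or the last visit attended. Under the first reading, a participant whose last dose was on a test cycle restarts off-test. Under the second, a participant whose last dose was on an off-test cycle does. Either way some restarts land off-test. If the resumed visit is a test cycle, the test falls on the restart day and there is no problem.

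**Step 3: age of the last scheduled test at an off-test restart.** Once the 30-day visit has passed, age = gap − 30 (±5).

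| Gap since last dose (days) | Age of last scheduled test (days) |
|---|---|
| 42 | 42 − 30 = 12 (7 to 17) |
| 61 | 61 − 30 = 31 (26 to 36) |
| 90 | 90 − 30 = 60 (55 to 65) |
| 180 | 180 − 30 = 150 (145 to 155) |

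Only the 61-day row is tied to a period in the protocol, the contraception minimum. The other rows are illustrations, because the documents give no distribution of gaps.

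**Step 4: when is this worse than continuous treatment?** The age exceeds the on-treatment maximum once the gap passes 30 + 14 = 44 days (39 to 49) on 2-week cycles, or 30 + 21 = 51 days (46 to 56) on 3-week cycles. Between about 30 days and those thresholds, the 30-day test is no older than a test can be on continuous treatment.

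**Step 5: upper limit and next test.** Section 6.7 sets no maximum gap for a restart after progression or after a resolved AE, other than the end of the study. After an off-test restart dose the next scheduled test comes one cycle later, at 14 or 21 days.

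**The case against.** The strongest reply is that the protocol leaves the matter to the Investigator and does not neglect it. The laboratory precondition in Section 6.7 is open-ended and could be read to include hCG. The same section provides for case-by-case work-up and a benefit-risk confirmation. Section 8.2.4 allows additional tests at any time, so its link to the Table 1 time points does not rule out a pre-restart hCG. Section 5.1 asks that a suspected pregnancy be reported at once, before any test. It requires contraception during study intervention, which applies again on restart, and its 28-day lead-in may also be read to apply. The 2 months is a floor. Finally, a site that tests at the resumed visit is within the plan, because Table 1 does not fix the tested cycles.

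All of this stands, and it limits the point. None of it requires a test: each item is discretionary, or concerns contraception or reporting.

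A reader might go further and infer three things that the documents do not support.

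- That the schedule forces an untested restart. It does not; it permits one.
- That restarts at 12 weeks are contemplated, with a test 84 − 30 = 54 days old, because Section 7.1 says of persistent Grade 3 treatment-related AEs that if they do not improve "within 12 weeks after last dose of study intervention, treatment must be permanently discontinued". That rule most naturally describes a dose hold, not the discontinue-and-restart path of Section 6.7. For missed visits Section 6.6 asks sites to attempt the Table 1 assessments, so pregnancy tests would still be attempted during a hold. The 12-week limit is not a benchmark for the restart gap.
- That women restarting after 2 months will be without contraception. Only the stated minimum has ended by then.

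**Conclusion.** The point holds in a limited form. For courses restarted within the rollover study, no passage expressly requires a pregnancy test before the first dose. A restart can comply fully with the protocol with no test since the 30-day visit. At a 61-day gap that test would be about 31 days old (26 to 36), compared with at most 14 or 21 days on continuous treatment, and it ages day for day with longer gaps.

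This rests on three assumptions: the cycle count continues across the gap, as Section 6.7 indicates; the resumed visit is an off-test cycle; and the site adds no discretionary test. It also takes the 30-day test as done. A Table 1 note lets Safety Follow-up visits be telephone calls where necessary, in which case even that test could be missed.

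The documents give no count of women of childbearing potential or of restarts. With the protocol estimating at least 10 participants in all, the number affected is likely very small. No endpoint or analysis changes. I rate this minor: a cheap safety improvement.

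**What to change.** Add a line to the pre-restart list in Section 6.7 and to the pregnancy row of Table 1. It should require a negative urine or serum hCG test in women of childbearing potential before the first dose of any restarted course, whatever the cycle number. State that alternate-cycle testing is then counted from that test, which also settles how the alternation resumes. The age of the last test at restart would then be set by that test's window, 0 days if done on the day of dosing, whatever the gap.

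The cost is two lines of text and one hCG test per restart in women of childbearing potential. The SAP needs no change.

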2.2 Background

Bintrafusp alfa is being developed as an immuno-oncology agent for treatment in a number of tumor types, including non-small cell lung cancer (NSCLC), biliary tract cancer (BTC), cervical cancer, and triple-negative breast cancer (TNBC). Bintrafusp alfa is designed to simultaneously target 2 pathways that have independent and complementary immunosuppressive functions in the tumor microenvironment. Programmed-death ligand 1 (PD-L1) signaling plays a key role in the immunosuppressive network that dampens T-cell activity and TGF β functions as an autocrine or paracrine signal within the local tumor microenvironment, where it promotes tumor progression.

The novel design of bintrafusp alfa, which binds all 3 isoforms of TGF β and simultaneously inhibits the anti-PD-L1 pathway in the tumor microenvironment, may be more effective than agents targeting PD-L1 and TGF β separately. Nonclinical experiments conducted by the Sponsor ([Lan 2018](#)) demonstrated that bintrafusp alfa strongly enhances antitumor activity and prolongs survival in mouse tumor models above the effect of either an anti-PD-L1 control antibody or the TGF β Trap control alone (at the same molarity as bintrafusp alfa).

The overall safety profile of bintrafusp alfa at 1,200 mg every 2 weeks as a monotherapy in close to 700 participants with various cancer types is manageable; no new safety signals emerged in the 2 Phase I studies (EMR200647-001 and MS200647-0008) compared with therapies targeting PD-L1 or TGF β . Albeit limited experience to date, the safety profile in participants treated at a dose level of 2400 mg every 3 weeks appears to be consistent with the safety profile in patients treated at lower doses.

In addition, currently available safety data on bintrafusp alfa in combination with chemotherapy indicated no increased risks compared to what can be expected from current experience with chemotherapy and bintrafusp alfa alone.

2.3 Benefit/Risk Assessment

Bintrafusp alfa, a first-in-class bifunctional fusion protein that targets the tumor microenvironment where it blocks both the cell intrinsic programmed cell death protein 1 (PD-1)/PD-L1 interaction and the immunosuppressive TGF β , is hypothesized to be more effective than agents that target only a single pathway. With the clinical activity of bintrafusp alfa observed in a number of tumor types, including NSCLC, biliary tract cancer, cervical cancer, and TNBC, together with the safety profile that appears to be manageable given the advanced disease of the studied populations, the benefit/risk evaluation is considered favorable to conduct this rollover study. The emerging safety profile of bintrafusp alfa across tumor types is manageable and consistent with other therapies targeting either PD-L1 (Brahmer 2012, D'Angelo 2018 and Kelly 2018) or TGF β pathways (mainly referencing Phase I fresolimumab clinical study; Morris 2014). The risks of bintrafusp alfa are classified as presented in [Table 2](#).

The data review outcome from the 3 randomized controlled studies in NSCLC and BTC (MS200647_0037 [NCT03631706], MS200647_0055 [NCT04066491] and MS200647_0005 [NCT03840902]), which have been discontinued in the course of 2021, appears to indicate, consistently across 2 indications, either poorer observed hazard ratios for progression free survival (PFS) and OS in the experimental arms with bintrafusp alfa or low likelihood for bintrafusp alfa to add benefits compared to standard of care. No new safety signal has been identified. The data review also showed that cases of early progression and death (i.e., within 60 days after start of treatment) were observed more frequently with bintrafusp alfa: 16 patients (10.6%) versus 9 patients (5.9%) in NSCLC Stage IV first line (bintrafusp versus pembrolizumab, MS200647_0037); 11 patients (7.5%) versus 2 patients (1.3%) in BTC first line (bintrafusp in combination with chemotherapy versus placebo plus chemotherapy, MS200647-0055); immature data with 3 patients (4.1%) versus 2 patients (2.6%) in NSCLC Stage III (bintrafusp plus concurrent chemoradiation followed by bintrafusp maintenance versus chemoradiation followed by durvalumab, MS200647-0005). Early deaths were due to progressive disease, signs and symptoms of progressive disease, or known treatment toxicities.

Two types of participants will be eligible for this study: participants on treatment with bintrafusp alfa in an eligible parent study after the primary/main analysis has been completed, and participants who have discontinued treatment in an eligible parent study and are reinitiating treatment in this rollover study (provided that the parent protocol allows reinitiation of treatment). Participants continuing treatment in the rollover study and demonstrating benefit from the active treatment will be transferred from the parent study to this rollover study. Participants reinitiating treatment in the rollover study have previously demonstrated benefit from bintrafusp alfa and reinitiation is deemed a reasonable option that may provide clinical benefit. Based on the available nonclinical and clinical data to date, inclusion in the rollover study, as specified in this protocol, is considered justifiable for both groups.

Of note, participants that are reinitiating after discontinuing their prior course of bintrafusp alfa treatment due to an adverse event (AE) are required to have that AE completely resolved or well

controlled, and the decision to reinitiate must be discussed with the Medical Monitor prior to enrollment to determine the suitability of the participant. This discussion should confirm the status of the AE and confirm that the likelihood of recurrence/worsening of the AE that led to the prior discontinuation is low. The outcome of the discussion will provide an opportunity to weigh the risk against prior benefit demonstrated while on treatment and assess the benefit-risk for individual participants prior to enrollment.

More detailed information about the known and expected benefits and risks and reasonably expected AEs of bintrafusp alfa may be found in [Section 2.3.1](#) and the current IB.

Based on the available nonclinical and clinical data to date, the conduct of the study, as specified in this protocol, is considered justifiable.

